Study protocol

Title : Impact of a coronary artery calcium-guided primary prevention of major coronary heart disease for asymptomatic coronary artery disease in diabetes: a prospective cohort study

PI: [name]

CO-PI: [name], [name]

Affiliations

Cardiovascular center, Lo-Tung Poh-Ai Hospital, Taiwan

Version 2, 12/09/2021

Background

The patients with type two diabetes mellites increased gradually and heart disease and cerebral vascular disease is the fourth leading cause of mortality.

According to the National Health Insurance Research Database (NHIRD) till 2014, incidence of coronary heart disease is 25.2% and heart failure is 3.77% . Multiple complication including chronic kidney disease and cerebrovascular diseases were also well-known.

A systematic review study of scientific evidence from across the world in 2007-2017 revealed cardiovascular disease (CVD) affected 32.2% overall; 29.1% had atherosclerosis, 21.2% had coronary heart disease (CAD), 14.9% heart failure, 14.6% angina, 10.0% myocardial infarction and 7.6% stroke. CVD representing 50.3% of all deaths is a major cause of mortality among people with type 2 Diabetes mellitus (T2DM) (1).A study in Asian population revealed patients with diabetes had a 1.89-fold risk of all-cause death and 2.0-fold risk of cardiovascular death compared with patients without diabetes(2) . However, most diabetes with CAD are asymptomatic.

Coronary artery calcium (CAC) score measured by multi-detector computerized tomography is a reliable measure of subclinical atherosclerosis.

The presence, extent and progression of CAC have been shown to predict adverse cardiovascular events better than traditional risk factors and global risk scoring (3-7) . Our previous study in 2020 revealed CAC score could predict long-term cardiovascular outcomes in asymptomatic patients with T2DM (8). 2019 AHA/ACC Guideline on the Primary Prevention of Cardiovascular Disease and 2019 ESC/EAS Guidelines for the management of dyslipidaemias recommend CAC score as a decision making aid for personalized risk management in primary prevention (9,10). This prospective cohort study will investigate the impact of a coronary artery calcium-guided primary prevention of major coronary heart disease for asymptomatic coronary artery disease in T2DM.

Objective

To evaluate benefits of primary prevention of major coronary heart disease for asymptomatic coronary artery disease in T2DM based on the coronary artery calcium score

Our proposal

1. Based on CAC score, primary early prevention could reduce incidence of major coronary heart disease (CHD) including cardiac mortality, acute myocardial infarction, coronary revascularization

2. based on CAC score, primary early prevention could reduce all cause mortality, cardiac mortality, cardiovascular disease, heart failure, ischemic stroke, heart failure associated hospitalization and chronic kidney disease and related clinical cost effect.

Method

Population:

The investigators will enroll 1500 asymptomatic T2DM patients who will receive Coronary artery calcium (CAC) imaging using 256 sliced multi-detector computerized tomography (MDCT) scanner as research group and 500 patients as control group from Lan-Yan Diabetes Shared Care Network (public health bureau, clinics, and regional hospital in Yilan County).

Inclusion criteria: more than 40 years old T2DM patients have any one cardiovascular risk as follows

1. total cholesterol > 200 mg/dl or low density lipoprotein (LDL) > 100 mg/dl
2. blood pressure $> 140/90$ mm/Hg or taking anti-hypertension agents
3. history of smoking
4. family history of early coronary heart diseases
5. proteinuria

Exclusion criteria: history of cardiovascular diseases such as coronary heart disease, stroke, heart failure etc, pregnant

CAC Scores Measurement

Coronary artery calcium (CAC) imaging was performed using an 256 sliced multi-detector computerized tomography (MDCT) scanner (Philips Brilliance 256) equipped with high-resolution detectors.

Intervention for study group

Based on 2019 AHA/ACC Guideline on the Primary Prevention of Cardiovascular Disease and 2019 ESC/EAS Guidelines for the management of dyslipidemias and result of CAC score(9-12), the investigators will recommend the in-charged doctor to control the cardiovascular risk factors more aggressively. The study protocols are as follows

If CAC score >0 , Treadmill ECG or Thallium²⁰¹ Scan would be arranged. If Treadmill ECG or Thallium²⁰¹ show significant ischemia, further study such as CT angiography or coronary angiography will be arranged.

If CAC score > 100 , Aspirin 100mg QD will be suggested to decrease the cardiovascular risk in patients with low risk of bleeding. Previous studies revealed aspirin for patients with CAC score >100 at low bleeding risk indicated net benefit (13-17).

If CAC score > 400 , statin therapy will be suggested to control lipidemia aggressively and target LDL level <70 mg/dL (9-12) °

The investigators will follow up these patients every 6 month, record their results of blood tests and medication for 5 years. Primary endpoint is major coronary heart disease including cardiac mortality, acute myocardial infarction and coronary revascularization. Second endpoint include all caused death, death due to cardiovascular disease, heart failure, stroke, admission for heart failure, chronic kidney disease and stroke, and cost related to AMI, coronary heart disease, heart failure, stroke, chronic kidney disease etc.

Control group

The investigators will enroll 500 age, gender, risk factor matched T2DM patient from our hospital. The doctor in charge will give usual care according to the Diabetes associate of Taiwan clinical practice guidelines for diabetes care.

Reference

3. Dedic A, Ten Kate GJ, Roos CJ et al. Prognostic Value of Coronary Computed Tomography Imaging in Patients at High Risk Without Symptoms of Coronary

- Artery Disease. *The American journal of cardiology* 2016;117:768-74.

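### Coronary revascularization is an unqualified primary event, but ischemia testing and angiography are arranged only in the study group, so procedures prompted by that work-up may count mainly there

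*Protocol*

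**What the plan says.** The last paragraph of Intervention for study group defines the endpoint: "Primary endpoint is major coronary heart disease including cardiac mortality, acute myocardial infarction and coronary revascularization". Revascularization is not limited by symptoms, urgency, timing or what led to it. Item 1 of Our proposal predicts a reduction in this same composite.

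The same section sets out a stepwise work-up for the study group. It begins "If CAC score >0 , Treadmill ECG or Thallium" (a thallium-201 scan). If the test results "show significant ischemia, further study such as CT angiography or coronary angiography will be arranged".

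The Control group section arranges no calcium scan, ischemia test or angiography: "The doctor in charge will give usual care according to the Diabetes associate of Taiwan clinical practice guidelines for diabetes care". These controls are matched, not randomized: "The investigators will enroll 500 age, gender, risk factor matched T2DM patient from our hospital".

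On data collection, the follow-up sentence says the investigators will "record their results of blood tests and medication for 5 years". Two components of the composite can be looked at separately. Item 2 of Our proposal lists cardiac mortality as an outcome of its own ("primary early prevention could reduce all cause mortality, cardiac mortality, cardiovascular disease, heart failure, ischemic stroke"), and acute myocardial infarction has to be identified for the secondary endpoint of "cost related to AMI, coronary heart disease, heart failure, stroke, chronic kidney disease etc".

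**The concern.** Participants are symptom-free and have no cardiovascular history, and the Background says that coronary disease in diabetes is mostly silent. The strategy under test looks for that silent disease in one group only. If a finding leads to revascularization, the procedure counts as a failure of the strategy. A control with the same disease counts only if it surfaces through symptoms, an event or testing in usual care.

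One component of the composite can thus be raised by detection while the others are lowered by prevention. A null or unfavourable composite could then mean no benefit, or a benefit partly offset by prompted procedures. This bias alone leans against the study group. The controls are not randomized, however, so the direction of the net bias is unknown, and a favourable result is not made safe by this argument.

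**Working it through.** The protocol gives group sizes (1500 and 500) but no event rate, effect size or power, so there is no stated calculation to reproduce. The mechanism follows from the sections cited above. The arithmetic below only shows how large the effect could be.

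**Prompted procedures in the study group.** All three proportions are assumptions.

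x = P(calcium score above 0) × P(ischemia) × P(revascularization)

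- Low: 0.5 × 0.05 × 0.2 = 0.005, or 8 of 1500
- Mid: 0.6 × 0.125 × 0.3 = 0.0225, or 34 of 1500
- High: 0.7 × 0.2 × 0.4 = 0.056, or 84 of 1500

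**Observed risk ratio.** Further assumptions:

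- The true risk ratio is 0.75.
- p0 is the control risk without prompted procedures.
- c is the rate of prompted procedures per control patient, relative to the study group.
- q1 and q0 are the shares of prompted patients, in the study and control groups, who would have had another primary event anyway. They are set either to average risk (q1 = 0.75·p0, q0 = p0) or to 0.40 in both groups.

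Observed RR = [0.75·p0 + (1 − q1)·x] / [p0 + (1 − q0)·c·x]

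Example with p0 = 0.10, c = 0, mid-range x and average risk: (0.075 + 0.925 × 0.0225) / 0.10 = 0.96.

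Results at p0 = 10%:

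| c | Overlap | Low | Mid | High | Procedures in 1500 that bring the ratio to 1 |
|---|---|---|---|---|---|
| 0 | average risk | 0.80 | 0.96 | 1.27 | 41 |
| 0 | 0.40 | 0.78 | 0.89 | 1.09 | 63 |
| 0.25 | average risk | 0.79 | 0.91 | 1.13 | 54 |
| 0.25 | 0.40 | 0.77 | 0.86 | 1.00 | 83 |
| 0.5 | average risk | 0.78 | 0.87 | 1.01 | 79 |
| 0.5 | 0.40 | 0.77 | 0.83 | 0.93 | 125 |

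The break-even for the first row is 0.025 / 0.925 = 0.027, and 0.027 × 1500 is about 41.

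**Higher control risk.** The Background gives a coronary heart disease incidence of 25.2% without a time frame. With p0 = 25.2% and the high x, the ratio is 0.93 (average risk) or 0.88 (0.40) when c = 0, and 0.86 or 0.83 when c = 0.5. The benefit is diluted, not reversed.

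**Cruder cross-check.** With no overlap and no prompted procedures in controls, the benefit is cancelled when x = p0 × (1 − true RR). For control risks of 5% to 15% and true ratios of 0.7 to 0.8, this runs from 0.05 × 0.2 = 1.0 point (15 of 1500) to 0.15 × 0.3 = 4.5 points (about 68 of 1500). This is the harshest version of the model.

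**The case against.** The strongest reply is that this is a familiar limitation of strategy studies, not an error. Several parts of that reply stand:

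- Total revascularization is a legitimate strategy outcome, and item 1 of Our proposal names it.
- The protocol stops at angiography. That some patients are then revascularized is an inference.
- Usual care does not bar testing, so controls may also have prompted procedures.
- The size rests wholly on assumptions. Every mid-range result is below 1, and at 10% control risk ratios above 1 are seen only at the high setting of all three proportions.
- This bias would not manufacture a false benefit.

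The recording argument is also weaker than it may look. The follow-up sentence cannot be an exhaustive list, since it also omits deaths, infarctions and the procedures themselves. Study-group tests are arranged by the protocol and should be traceable, and source records may show the indication in both groups. Still, classification after the fact may differ between a group under protocol work-up and one in usual care. The safeguard is to record the reason at the time.

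Supportive analyses are often left to a statistical analysis plan, and one may exist. But the unqualified endpoint and the one-sided work-up are both fixed in the protocol, and an analysis plan can use the reason for a procedure only if it was captured.

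Finally, a class for procedures that followed testing is loose without a time limit, and staff who know the group would assign it. That calls for a tight written definition; it does not remove the problem.

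**Conclusion.** The concern holds and should be fixed. Followed as written, the plan can add detection-driven primary events mainly in the study group, and nothing else in the protocol corrects for this. The mechanism is clear from the text, but the size is not, so confidence is medium. With a true ratio of 0.75, a 10% control risk and no prompted procedures in controls, an apparent 25% reduction shrinks to 4–11% at mid-range, and 41 to 63 procedures (2.7–4.2% of the study group) erase it. Across all the assumptions shown, the effect runs from trivial to cancelling or reversing the benefit.

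**What to change.** Keep the composite as the primary endpoint and amend the endpoint section in three ways.

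1. For each revascularization in both groups, record on the same form and by the same definitions whether it followed testing in a symptom-free patient (by protocol or in usual care), symptoms, or an acute coronary syndrome. Fix in advance how long after a test a procedure still counts as prompted.
2. Pre-specify cardiac mortality plus acute myocardial infarction, which the work-up does not directly inflate, as the key analysis beside the composite.
3. Report the composite with and without procedures prompted by testing in symptom-free patients. State that the version with them leans against the study group. State also that the version without them can favour it, because disease treated after the work-up goes uncounted while the same disease in a control counts once symptomatic. The two versions bracket the problem; they do not remove it.

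The cost is a short amendment and one extra item per revascularization; no masked reviewer is required. The key analysis is less precise. At a 10% control risk and a ratio of 0.75, the composite gives 50 control and about 113 study-group events. If cardiac death plus infarction makes up half of these (assumption), about 25 and 56 remain. The 95% interval factor is exp(1.96 × √(1/e0 − 1/500 + 1/e1 − 1/1500)), where e0 and e1 are the control and study-group events. It widens from about 1.37 to 1.58, or to between 1.52 and 1.68 if the share is 60% to 40%.

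### Controls are matched on factors the protocol ranks below CAC and no scan is planned for them, so the comparison supports association rather than reduction

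*Protocol*

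**What the plan says.** The Background of the protocol gives the design: "This prospective cohort study will investigate the impact of a coronary artery calcium-guided primary prevention of major coronary heart disease". No section describes randomisation or any other rule that decides who enters which group.

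The study group is defined under Method, Population: "The investigators will enroll 1500 asymptomatic T2DM patients who will receive Coronary artery calcium (CAC) imaging". The same paragraph takes "500 patients as control group from Lan-Yan Diabetes Shared Care Network". The Control group section describes the controls again, with a different source: "The investigators will enroll 500 age, gender, risk factor matched T2DM patient from our hospital". It adds: "The doctor in charge will give usual care according to the Diabetes associate of Taiwan clinical practice guidelines for diabetes care". The scan is mentioned only for the study group.

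On prognosis, the Background says that the presence, extent and progression of "CAC have been shown to predict adverse cardiovascular events better than traditional risk factors and global risk scoring".

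The first hypothesis, under Our proposal, is causal: "Based on CAC score, primary early prevention could reduce incidence of major coronary heart disease (CHD", followed by the components of the primary endpoint. The second is worded in the same way for the secondary outcomes.

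**The concern.** Matching balances what it matches on. Here that is age, gender and an unspecified set of risk factors, which are the kind of predictors that the protocol says CAC outperforms. CAC itself is known for 1500 patients and, as the plan is written, for none of the 500 controls. Patients with the same age, gender and risk factors can still differ in CAC, and nothing in the plan makes that remaining difference average out between the groups.

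If the groups differ in underlying CAC, the difference appears in the primary comparison as an effect of the programme. An analysis plan can adjust for measured covariates, but not for a CAC score that controls do not have. A conclusion that the programme reduces major coronary heart disease would then rest on an assumption the study cannot test.

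**Working it through.** The protocol gives no CAC distribution, event rate, effect size, significance level or power, so it has no figure to reproduce. The calculation below only shows how large the problem could be.

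**Inputs from the protocol:** 1500 study patients, 500 controls, 5 years of follow-up.

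**Assumed inputs (not in the protocol):**
- *ps*, *pc*: share with CAC above 100 in the study and control groups. Only imbalance left after matching counts. Gaps of 5 and 10 points are shown in both directions.
- *R*: event rate ratio, CAC above 100 against 100 or below, conditional on the matched factors. Range 3 to 6.

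**Formula** for one unmeasured binary confounder:

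apparent rate ratio = true rate ratio × [1 + *ps*(*R* − 1)] / [1 + *pc*(*R* − 1)]

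**No true effect:**

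| *ps* v *pc* | *R* = 3 | *R* = 4 | *R* = 6 |
|---|---|---|---|
| 25% v 30% | 1.50/1.60 = 0.94 | 1.75/1.90 = 0.92 | 2.25/2.50 = 0.90 |
| 25% v 35% | 1.50/1.70 = 0.88 | 1.75/2.05 = 0.85 | 2.25/2.75 = 0.82 |
| 30% v 25% | 1.60/1.50 = 1.07 | 1.90/1.75 = 1.09 | 2.50/2.25 = 1.11 |
| 35% v 25% | 1.70/1.50 = 1.13 | 2.05/1.75 = 1.17 | 2.75/2.25 = 1.22 |

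**Hiding an effect.** With an assumed true rate ratio of 0.75 and 35% v 25%, the apparent ratio is 0.75 × 1.13 = 0.85 at *R* = 3, 0.88 at *R* = 4 and 0.92 at *R* = 6.

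**Effect on a significance test.** Take a spurious ratio of 0.85 (25% v 35%, *R* = 4), 1500 v 500 patients and a two-sided test at 0.05. The chance of declaring a significant benefit when there is none is 0.11, 0.18 or 0.26 for assumed 5-year control risks of 5%, 10% or 15%. The nominal chance in that direction is 0.025.

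**Turning the formula round.** The control prevalence that would fully explain an observed ratio *RRobs* is

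*pc* = {[1 + *ps*(*R* − 1)] / *RRobs* − 1} / (*R* − 1)

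For example, with *RRobs* = 0.80 and *ps* = 25%:
- *R* = 3: (1.50/0.80 − 1)/2 = 0.875/2 = 44%.
- *R* = 6: (2.25/0.80 − 1)/5 = 1.8125/5 = 36%.

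A gap of 11 to 19 points would be needed. The study can report this quantity from its own scans together with a range of *R*.

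**The case against.** The strongest reply is that this is a disclosed cohort study. Residual confounding comes with that design, a cohort may pose a causal question, and the hypotheses are worded tentatively. That stands as far as it goes: a cohort is not an error in itself. What remains is that the claim is one of reduction, while the balancing method leaves out the predictor that the protocol ranks highest and the plan does not collect it in controls.

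A second reply is that the statistical analysis plan, which was not available, may deal with confounding. It may, for measured covariates, and it may already contain a bias analysis. It cannot supply CAC scores for unscanned controls.

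A third is that every input to the calculation is assumed. That is correct. Matching may also remove part of any CAC difference, so the real gap could be smaller than those shown.

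Some stronger readings are tempting, but the documents do not support them:
- A reader might infer that the investigators, doctors or patients choose who is scanned. The protocol does not say how patients come to be in either group.
- A reader might infer that the bias favours the programme. Nothing in the text fixes a direction, and equal gaps either way give distortions of similar size.
- A reader might infer that the study cannot inform its question at all. The study group's CAC data allow a calculation of how much imbalance would explain the result, so the finding can be graded, though not proved causal.

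**Conclusion.** The point holds as a limit on what may be concluded. As written, a lower event rate in the scanned group could reflect the programme, a CAC difference left after matching, or both, and the planned data cannot measure that difference directly. With a 10-point gap in CAC above 100 (25% against 35%) and a rate ratio of 3 to 6, the apparent rate ratio under no effect is 0.82 to 0.88 in one direction and 1.13 to 1.22 in the other. A 5-point gap gives 0.90 to 0.94 or 1.07 to 1.11.

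These figures rest entirely on assumed prevalences and rate ratios. Two readings of the text are inferred from silence: that allocation is not random, and that controls are not scanned. The two stated sources of controls add a possible route to imbalance if the Control group section is the one followed, because controls from a single hospital may differ in case mix from scanned patients drawn from the wider network.

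**What to change.** 1. State the primary and secondary hypotheses, and the conclusions to be drawn from them, as association (CAC-guided prevention is associated with a lower incidence) instead of reduction.
2. Prespecify a quantitative bias analysis of the primary result. Use the study group's CAC distribution and the inverted formula above to report how large a CAC difference in controls would explain the observed effect. Show a range of CAC-specific rate ratios, because the study group's own rates come from patients who were treated and investigated further on the basis of their score. Interpret the result as supporting benefit only if the required difference is implausible by a criterion fixed in advance.
3. Reconcile the source of controls between Method, Population (the shared care network) and the Control group section (the investigators' hospital), so that both groups come from the same source.

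Items 1 and 2 cost a weaker claim, some rewording and a small extra analysis on data already planned. Item 3 is a correction of the text, but may change where controls are recruited.

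Random assignment of patients not yet enrolled would be stronger. It is a redesign for the sponsor to consider and not a required change. It would need a protocol amendment and new consent wording. Because the intervention is advice to the treating doctor, contamination between groups would also need thought. The protocol does not show whether enrolment has begun, so it may no longer be possible.
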